## Study Methods

**Study Design.** Population based case-control point-prevalence study.

### Estimated Sample Size “Power analysis”

**Aim: Primary aim.** To investigate the prevalence of AAA in adult offspring to AAA patients compared to controls. **Hypothesis** The prevalence of AAA in adult offspring to AAA patients is higher than in persons in the population.

**Power analysis.** We estimate the participation rate to be lower than in the population-based screening (80%) due to lower age in invited adult offspring ; approximately 65%. Therefore an additional 200 women and 180 men will be invited, in order to obtain the examined persons below.

MEN: POWER: Alfa 0.05; power 0.80; estimated prevalence 7 % in offspring, 1.0% in controls; minimum of 166 persons in each group is requested. (men). 65% participation.

Invitation: 100 persons more: **350 invited men in offspring and 350 in control group**

WOMEN: POWER: Alfa 0.05; power 0.80; estimated prevalence 5 % in offspring, 0.5% in controls; minimum of 206 persons in each group is requested. 65% participation.

Invitation: 100 persons more: **400 women in offspring and 400 in control group.**

Table 1. Study assessments.

Visit	Baseline
Time window	At US
Informed consent	X

Demographic data	X
Medical history and clinical examination	X
Concomitant medication	X
US Aortic diameter	X
Questionnaires	X
Cases referred to vascular center	

aAge, sex, civil status, education level. b Current medical conditions and medical history, blood pressure, ankle-brachial index, pulse, height and weight. c Creatinine (mmol/L). d HADS and EQ-5D and self reported knowledge of AAA risks.

### General Analysis Considerations

Final analyses will be performed when lowest possible number of participants have been examined.

Continuous checks on participation is performed according to power calculation.

Invitations are however sent two weeks before examination.

All data will be deidentified and transferred to an SPSS file for statistical analysis.

The Adult offspring or control, women and men will be presented separately. Missing cases, non-participants will be presented. Index persons, their parents with AAA will be presented with sex and age at AAA diagnosis.

Multiple imputations or random effects models will not be used.

Per protocol analysis will be performed, based on the four groups; sex (2) and heredity (yes/no).

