### Introduction

AAA is an asymptomatic widening of the infrarenal aortic diameter to  $\geq 3$  cm. Male sex, increasing age, and heredity are important non-modifiable risk factors for development of the disease. This multifactorial disease has life-threatening consequences; if rupture occurs, mortality is 100 % if left untreated. The risk for rupture is closely related to the size of the AAA, and identification of patients with smaller AAA is therefore crucial. Fewer women than men in the population have AAA (1:5) but women diagnosed with AAA suffer a higher aneurysm growth rate, higher rupture risk, higher complication rate when treated, and have a more challenging aneurysm anatomy. Women are not included in any national screening program.

In 2016 the Swedish National Board of Health and Welfare (NBHW) published guidelines recommending population based screening of 65-year old men, based on a reported 40% reduction in aneurysm-related death in screened men. We have recently reported on the 4% annual decline in aneurysm mortality in invited men. The incremental cost-efficiency ratio was 8000 Euro/QALY. (Circulation, Wanhainen, 2016).

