### Study Objectives and Endpoints

**Aim: Primary aim.** To investigate the prevalence of AAA in adult offsprings to AAA patients compared to controls, stratified by sex

**Hypothesis** The prevalence of AAA in adult offsprings to AAA patients is 4-fold higher than in persons in the population.

**Secondary aim.** To investigate the awareness of the hereditability for AAA in adult offspring to AAA patients compared to controls, including anxiety levels.

**Hypothesis** The adult offspring to AAA patients have a low awareness of AAA risk, but higher than persons in the population.

**The third aim** is to evaluate the cost efficiency of the program, compared to sibling screening and screening in 65-year old men.

[figure not shown]
**Hypothesis** The selective registry-based screening in adult offsprings to AAA patients is as cost-efficient in detection of persons at risk as the program for 65-year old men.

**Fourth Aim.** To evaluate the registrybased detetion model- an evaluation of the feasibility.

**Hypothesis** The selective registry-based screening can be effective and work in a national setting.

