### Summary of Study Data

All continuous variables will be summarized using the following descriptive statistics: n (non-missing sample size), mean and standard deviation. The frequency and percentages (based on the non-missing sample size) of observed levels will be reported for all categorical measures. In general, all data will be listed, sorted by groups and stratified by sex. All summary tables will be structured with a column for each group (Adult offspring or control, women and men). Primary endpoint; prevalence will be presented for each strata and group. They will be presented also for age groups.

Demographic variables, concurrent illnesses and baseline variables are outlined as usual. Their apprehension of their risk for disease will be presented for the four groups also including their data on the index person.

Derived variables to be included in the analyses are the subscales of the HADS instrument, HADS-Anxiety (HADS-A) and HADS-Depression (HADS-D) as well as the subscales of the EQ-5D.

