### Efficacy Analyses

$\chi^2$  test will be used to analyse categorical variables and independent *t* test to analyse continuous data. For comparisons of independent groups, Student's *t* test will be used for normally distributed data, and Mann-Whitney for non-parametric data or small samples. Categorical data will be analysed by Fischer's test where possible. Continuous variables are presented as means (SD), categorical variables are presented as counts and proportions as appropriate.

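### No age-adjusted offspring–control contrast is planned: add one supporting age-adjusted odds ratio per sex beside the crude comparison

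*Combined protocol and SAP*

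**What the plan says.** All references are to the combined protocol and SAP.

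- **Design and aim.** Study Methods describes a "Population based case-control point-prevalence study". The primary aim, under Study Objectives and Endpoints, is "To investigate the prevalence of AAA in adult offsprings to AAA patients compared to controls, stratified by sex". Allocation is not random, and sex is the only stratifier.
- **Age as a risk factor.** The Introduction says: "Male sex, increasing age, and heredity are important non-modifiable risk factors for development of the disease". A footnote to Table 1 lists "Age, sex, civil status, education level" as baseline data, so age will be on file for those examined.
- **Analysis groups.** General Analysis Considerations: "Per protocol analysis will be performed, based on the four groups; sex (2) and heredity (yes/no").
- **Tests.** Efficacy Analyses says the chi-square "test will be used to analyse categorical variables", and shortly afterwards assigns Fisher's test to the same kind of data. Neither carries a covariate.
- **Age in the tables.** After promising prevalence by stratum and group, Summary of Study Data adds: "They will be presented also for age groups". It gives no bands, no contrast within bands and no pooled estimate.
- **Regression.** Reporting Conventions has a rounding rule for regression coefficients, but no model is specified anywhere.
- **Ages of the two groups.** The only remark is in the sample size section: participation is expected to be lower than in population-based screening "due to lower age in invited adult offspring". The available text gives no sampling rule, age range or matching for controls.

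**The concern.** The study's main conclusion will be a difference in AAA prevalence between offspring and controls, attributed to heredity. If the examined groups differ in age, part of that difference, in either direction, belongs to age. Matching at invitation, if it exists, would not fully settle this: about 65% are expected to attend, and the plan itself links attendance to age, so balance among those invited need not carry over to those examined.

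The planned age-group tables could reveal an imbalance, but they give no estimate that allows for it. An adjustment chosen after seeing those tables would be post hoc. At stake are the size of the excess and its attribution, more than whether an excess is detected.

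**Working it through.** **1. The plan's own figures.** Inputs from the sample size section: alpha 0.05, power 0.80; men 7% vs 1.0%, women 5% vs 0.5%. With the pooled-variance formula for two proportions, two-sided and without continuity correction,

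n = [1.960·√(2p̄(1−p̄)) + 0.842·√(p₁(1−p₁)+p₂(1−p₂))]² / (p₁−p₂)²

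- Men, p̄ = 0.04: n = 166.3 (stated 166).
- Women, p̄ = 0.0275: n = 206.1 (stated 206).

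The stated numbers are therefore those of a crude comparison with no covariate. At 65% participation, 0.65×350 = 227.5 men (228 below) and 0.65×400 = 260 women would be examined per group.

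**2. Design odds ratios.** Men: (0.07/0.93)/(0.01/0.99) = 7.45. Women: (0.05/0.95)/(0.005/0.995) = 10.47.

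**3. Possible distortion by age (assumed).** The document gives neither an age gradient nor an age gap. Assume an odds ratio of 1.5 to 2.5 per 10 years and a gap of 3 to 5 years. The factor is approximately (odds ratio per 10 years)^(gap/10):

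- Smallest: 1.5^0.3 = 1.13.
- Largest: 2.5^0.5 = 1.58.

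The direction depends on which group is older. Stretching the assumptions to an odds ratio of 3 per 10 years and an 8-year gap gives a crude odds ratio of about 2.4 with no hereditary effect at all, still far below 7.45 and 10.47.

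**4. Sampling error.** SE of the log odds ratio = √[1/(np₁)+1/(n(1−p₁))+1/(np₂)+1/(n(1−p₂))]; 95% limits are a factor exp(1.96·SE) each way.

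| | n per group | SE | Factor | P(no control case) = (1−p₂)ⁿ |
|---|---|---|---|---|
| Men, minimum | 166 | 0.837 | 5.2 | 0.19 |
| Men, expected | 228 | 0.714 | 4.1 | 0.10 |
| Women, minimum | 206 | 1.038 | 7.7 | 0.36 |
| Women, expected | 260 | 0.924 | 6.1 | 0.27 |

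Expected control cases at the minimum n are 166×0.01 = 1.7 men and 206×0.005 = 1.0 women. With none, an ordinary maximum-likelihood odds ratio is infinite.

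**5. False positives.** By exact enumeration with no hereditary effect and offspring odds multiplied by 1.58, the two-sided rejection rate is at most 2.4% (Fisher) or 7.5% (chi-square, against 4.4% with no gap in the same setting).

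**6. Does adjustment work with so few cases?** Simulation of 2,000 runs per setting, assuming an odds ratio of 2 per 10 years and an age SD of 8 years, with Firth logistic regression with and without linear age. The true odds ratio at fixed age is 7.6 in men and 10.6 in women. Geometric mean odds ratios at the minimum n:

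| Offspring minus control age | Men, crude / adjusted | Women, crude / adjusted |
|---|---|---|
| 0 years | 7.1 / 7.2 | 8.7 / 8.9 |
| +5 years | 10.2 / 7.4 | 12.6 / 9.1 |
| −5 years | 5.1 / 7.3 | 6.4 / 9.1 |

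The crude estimate moves with the gap and the adjusted one stays put. Both are shrunk towards 1 by the method, more so in women.

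**7. Which crude test.** Exact power at the minimum n is 76.1% (Fisher) against 84.9% (chi-square) in men, and 77.4% against 86.1% in women, so the choice that Efficacy Analyses leaves open matters. One test per sex at 0.05 gives 1−0.95² = 9.75% for at least one false positive, if the two are independent.

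**The case against.** **The plan does look at age.** A reader might infer that nothing in the plan separates age from heredity. That goes too far: prevalence by group and age group is promised. What is missing is a contrast, adjusted or pooled over age. With one or two control cases expected per sex, the tables cannot supply it.

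**No imbalance is shown.** A reader might also infer from "due to lower age in invited adult offspring" that offspring are younger than controls. The sentence compares offspring with participants in population-based screening, not with this study's controls, and equal invitations per group are compatible with similar ages. Controls may be age-matched without the available text saying so. This objection stands: every figure in steps 3, 5 and 6 is conditional on assumed values.

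**The distortion is small beside the noise.** This is also true, and it limits the grade. It does not remove the point, because sampling error is shown in a confidence interval and an age imbalance is not.

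**Adjustment is not a remedy for power.** If offspring were younger, the crude test would lose power. A supporting model does not give it back, so lost power is no argument for this change.

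**Scale.** The hypothesis is a four-fold prevalence, not an odds ratio. At these prevalences the two are close: ratios of 7 and 10 against odds ratios of 7.45 and 10.47.

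**Conclusion.** The point holds in a limited form. In a non-randomised comparison, a risk factor that the plan names and records has no pre-specified place in the offspring–control contrast. Under the assumed gradient and gap, the crude odds ratio would be off by a factor of 1.13 to 1.58 either way, against sampling factors of 4.1 to 7.7. The stronger conclusion, that age could by itself generate the expected excess, is not supported: even the stretched assumptions reach only about 2.4. What remains is a risk to the size of the excess and to the statement that it reflects heredity independently of age. This should be corrected because doing so is cheap, but it does not threaten the study. If controls prove to be closely age-matched and balance holds among those examined, little of the concern is left.

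**What to change.** 1. State how controls are sampled, their age range and any matching.
2. Keep the crude comparison in each sex as primary. Name one test, chi-square or Fisher, and say how the two sexes are handled.
3. In General Analysis Considerations and Efficacy Analyses, pre-specify within each sex one supporting odds ratio with 95% CI from Firth-penalised (or exact) logistic regression of AAA on group and a single linear age term. Report it beside the crude prevalences and crude odds ratio whatever the result.
4. State in advance that this estimate neither replaces the primary test nor rescues a non-significant one. If its interval includes 1, the excess is not attributed to heredity independently of age on the crude result alone.

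The rule in item 4 is needed. In the simulation with equal ages, the adjusted interval excluded 1 while Fisher's test was non-significant in 3.6 to 8.6% of runs; the reverse occurred in at most 0.1%. With offspring 5 years older, the reverse occurred in 4.0 to 8.1%.

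Cost: a few lines of SAP text, one model per sex on data already collected, and some of the reviewing statistician's time. Sample size and the primary comparison are unchanged. The standard error rose by at most 0.019 at the design contrasts, so limits are up to exp(1.96×0.019) = 1.04 times as wide. With no hereditary effect it rose by at most 0.055 (1.11 times). The adjusted estimate will still be imprecise and somewhat shrunk, and should be presented as supporting only.

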### Summary of Study Data

All continuous variables will be summarized using the following descriptive statistics: n (non-missing sample size), mean and standard deviation. The frequency and percentages (based on the non-missing sample size) of observed levels will be reported for all categorical measures. In general, all data will be listed, sorted by groups and stratified by sex. All summary tables will be structured with a column for each group (Adult offspring or control, women and men). Primary endpoint; prevalence will be presented for each strata and group. They will be presented also for age groups.

Demographic variables, concurrent illnesses and baseline variables are outlined as usual. Their apprehension of their risk for disease will be presented for the four groups also including their data on the index person.

Derived variables to be included in the analyses are the subscales of the HADS instrument, HADS-Anxiety (HADS-A) and HADS-Depression (HADS-D) as well as the subscales of the EQ-5D.

### Efficacy Analyses

$\chi^2$  test will be used to analyse categorical variables and independent *t* test to analyse continuous data. For comparisons of independent groups, Student's *t* test will be used for normally distributed data, and Mann-Whitney for non-parametric data or small samples. Categorical data will be analysed by Fischer's test where possible. Continuous variables are presented as means (SD), categorical variables are presented as counts and proportions as appropriate.

### Reporting Conventions

P-values  $\geq 0.001$  will be reported to 3 decimal places; p-values less than 0.001 will be reported as " $<0.001$ ". The mean, standard deviation, and any other statistics other than quantiles, will be reported to one decimal place greater than the original data. Quantiles, such as median, or minimum and maximum will use the same number of decimal places as the original data. Estimated parameters, not on the same scale as raw observations (e.g. regression coefficients) will be reported to 3 significant figures.

### Quality Assurance of Statistical Programming

All statistical analyses will be performed in SPSS version 26, and in Stata (Version IC.16.1 Stata Corp, College Station, TX) when performed in collaboration with the reviewing statistician ([name], Uppsala). The reviewing statistician will have an overview of the entire analyses and will explicitly check the code producing tables 1, 2 and 3 as well as any other pieces of code as desired.

